As standard practice for psychology referrals at the MHSOP, the initial assessment will be completed primarily by [name], the Field Research Supervisor for the study. [name] will then screen psychology referrals for appropriate participants and inform them about the study. Following social distancing restrictions in place due to the SARS-CoV-2 outbreak, the MHSOP is currently only offering face-to-face appointments when necessary, offering telephone or videocall therapy appointment as a standard replacement. As such, the therapy in the current study will be offered by either telephone or videocall. At first contact, participants will be asked their preference and what technology provisions they have to facilitate videocalling (i.e. a smartphone or a laptop/PC with microphone and camera). The sessions will then be conducted using QHealth (MyMed Ltd, 2020), which is an NHS Digital and NHS England approved, centrally funded eConsultation supplier for the COVID-19 response. The therapeutic intervention will be conducted by the student researcher/therapist, [name]. Clinical supervision will take place between student researcher/therapist and [name] at the MHSOP. Weekly ACT supervision will be conducted between student researcher/therapist and Secondary Research Supervisor via telephone or face-to-face.

SELECTION OF PARTICIPANTS

ELIGIBILITY CRITERIA

To be eligible for the study, participants must have first been referred to the MHSOP for psychological support. The study will recruit both male and female participants, aged 65 years or older (there is no upper age limit).

Inclusion Criteria

1. Be at least 65 years of age.
2. Score at least 8 on the Hospital Anxiety and Depression Scale (HADS; Zigmond & Snaith, 1983) on either the anxiety or depression sub-scale. The HADS is an outcome measure already used by the MHSOP.
3. Be referred to the MHSOP for psychological support.
4. Have capacity to give informed consent.
5. Be willing to engage in one-to-one psychotherapy over telephone or videocall.

Exclusion Criteria

1. A score lower than 22-24 on the MoCA. This is to screen for a level of cognitive deficit, which cannot be accommodated for in the current study, due to the adaptations which will be required (e.g. review sessions, carer enrolment to support memory consolidation). Cut-off limit is dependent on the individual's age and education history. The MoCA is administered by the MHSOP as standard practice.

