2. Not rated higher than Cluster 8 (Mental Health Clustering Booklet 2013/14, Department of Health), a categorisation based on the Health of the Nation Outcome Scale (HoNOS; Wing et al., 1998). Clusters higher than 8 are associated with clients presenting with symptoms of psychosis and it is felt that this level of mental health problem would cause serious heterogeneity between client cases. As standard practice, the MHSOP at Ling Bar Hospital will have rated the client prior to consideration for the study.

3. Inability to understand English to a level required to participate fully in the intervention. This is due to a lack of ability to benefit from the intervention without an interpreter, and the impact an interpreter would have on the non-therapeutic processes (e.g. alliance) being measured in this study.
4. Not currently undertaking any other psychological therapy, talking therapy or counselling. This is due to the potential impact the other therapy could have on change and the inability to fully account for this.

Sampling and size of sample

The study will recruit up to four participants. Most Hermeneutic Single Case Efficacy Designs (HSCED) focus on one client (Stephen, Elliott, & Macleod, 2011). However, there have been recent calls to increase cross case synthesis to further validate the intervention being used (MacLeod, Elliott, & Rodgers, 2012). Three cases would fit with established guidelines for a single-case research series (Smith, 2012) and has shown to be feasible in previous HSCED research (e.g. Wall, Kwee, Hu, & McDonald, 2017). Drop-out or withdrawal would be a major concern with the current study, due to the extended participant contact time and the constraints on recruiting and treating further participants within schedule for Doctoral Thesis submission. With dropout rates around 25% (Grover, Dua, Chakrabarti, & Avasthi, 2018) recruiting up to four participants appears a sensible approach. **A fourth participant will only be recruited up until July 2020, to allow for the completion of the intervention and requirements of submission for the Doctoral Thesis.**

Sampling technique

The sample will be referrals from the MHSOP recruited in a convenience sampling method. As this study aims to reflect usual clinical practice, this is an adequate sampling method to recruit participants.

RECRUITMENT

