At the time of recruitment, all potential participants will be active referrals at the Rushcliffe Mental Health Service for Older People (MHSOP), Lings Bar Hospital, Nottinghamshire. They will also have been referred for further psychology support (i.e. any referral that is felt would benefit from individual clinical psychology sessions). Eligible clients (see inclusion/exclusion criteria) will be informed (through discussion and Participant Information Sheet) about the study during a psychology referral assessment with a Clinical Psychologist from the MHSOP ([name], Field Research Supervisor for the study), delivered by phone/videocall due to social distancing requirements. Adaptations such as larger font on sheets will be determined as well as whether they would be able to facilitate videocall therapy. Potential participants that are interested in taking part will have the CF and PIS posted out to them, with a follow-up call around a week later to obtain consent. Clients that do not consent to take part will be offered usual care from the service.

The Assistant Psychologist from the team will call those participants that consent to determine the dates of the intervention. The Assistant Psychologist will also go through a pack of questionnaires (Questionnaire Pack 1.1 [QP1.1]), which will have been posted out to them. This date will act as Baseline 1. The Assistant Psychologist will then call back a following three times, acting as Baselines 2, 3, and 4, all a week apart. Baseline 4 will ideally be the same day as the start of the Acceptance and Commitment Therapy (ACT) intervention. The ACT intervention will be conducted by the student researcher/therapist via telephone or videocall, depending on the participants wishes. Sessions will be audio recorded using an NHS encrypted electronic device, with participant knowledge, to conduct fidelity checks of the treatment at a later date. Participants will be supported to complete questionnaires after the session which will have been posted out to them.

Therapeutic sessions

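### Convenience sampling sets no order of approach and leaves no record of eligible clients passed over; offering places consecutively would close the gap at low cost

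*Combined protocol and SAP*

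**What the plan says.** The sample is small by design: "The study will recruit up to four participants" (Sampling and size of sample). Sampling technique then gives the method, "The sample will be referrals from the MHSOP recruited in a convenience sampling method", and the reason for it: "As this study aims to reflect usual clinical practice, this is an adequate sampling method to recruit participants".

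Study Setting describes the route in. "As standard practice for psychology referrals at the MHSOP, the initial assessment will be completed primarily by" the Field Research Supervisor, who, as the passage reads with names removed, "will then screen psychology referrals for appropriate participants and inform them about the study". What makes a participant appropriate is not stated at that point.

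Three other sections bear on the question:

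- **Screening and baseline** says that clients who are eligible, with a pointer to the inclusion and exclusion criteria, are told about the study at their psychology referral assessment.
- **Recruitment** gives the first approach to the client's usual care team.
- **Withdrawal** allows a discontinued participant to be replaced if time and therapist availability permit. It does not say how the replacement is found.

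**The concern.** The primary objective is the efficacy of ACT in distressed older adults, and the protocol justifies running several cases by the value of synthesis across them. With at most four cases, each is at least a quarter of the evidence. If the clinician who screens may choose among eligible clients, and no trace is kept of those not approached, a reader of the finished series cannot tell whether it shows the service's ordinary eligible referrals or a subset of them.

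The stated justification does not settle this. An aim to reflect usual practice is better served by taking eligible referrals as they come than by an unspecified choice among them.

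**Working it through.** **1. The plan's own figure.** The inputs are in Sampling and size of sample: three cases as the target ("Three cases would fit with established guidelines for a single-case research series") and dropout of about a quarter ("With dropout rates around 25" per cent).

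- Recruits needed: 3 / (1 − 0.25) = 4, which agrees with the stated maximum.
- Expected completers from four: 4 × 0.75 = 3.0.
- Chance that at least three of four complete, if dropouts are independent: 4 × 0.75³ × 0.25 + 0.75⁴ = 0.422 + 0.316 = 0.738.

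None of these depends on how clients are selected, so a change of sampling rule leaves the planned number alone.

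**2. The sections side by side.**

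| Question | What the readable text gives |
|---|---|
| Named method | Convenience (Sampling technique) |
| Who screens | A research-team member who also assesses referrals as routine (Study Setting) |
| Filter | 'Appropriate', undefined there (Study Setting); the listed criteria (Screening and baseline) |
| Order of approach | None stated |
| Record of eligible clients not approached | None stated |
| Order for replacements | None stated (Withdrawal) |

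Screening and baseline supports reading 'appropriate' as meeting the criteria. It does not say that every eligible client is informed in turn, and the convenience label suggests that this is not required.

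**3. Whether other safeguards reach selection.** Table 2 lists eight rival explanations: non-improvement, statistical artefacts, relational artefacts, client expectations, self-correction, life events, psychobiological factors and reactive effects. All concern change within an enrolled client; none concerns how the client entered the series. The adjudication panel works from the briefs, which exist only for enrolled clients. The four baselines likewise begin after consent.

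**4. Size.** Two inputs are missing: the number of eligible referrals (m), and the correlation (r) between the assessor's judgement and true prognosis. The following is an illustration only. It assumes normally distributed prognosis and the four most promising-looking of m clients taken together. The shift in mean prognosis is then r × (expected mean of the top four of m standard normal values).

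| m (assumed) | Mean of top four, SD | Shift at r = 0.2 | Shift at r = 0.5 |
|---|---|---|---|
| 4 | 0 | 0 | 0 |
| 6 | 0.48 | 0.10 | 0.24 |
| 8 | 0.73 | 0.15 | 0.36 |
| 12 | 1.02 | 0.20 | 0.51 |

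Under consecutive offer this judgement-driven shift is 0 for any m. The protocol describes clients being informed at their own assessment rather than chosen from a held pool, so the table is a generous model of what discretion could do.

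**The case against.** The strongest reply is that the operational text already limits discretion. Clients are informed at their own assessment, by reference to listed criteria that are mostly objective: age, HADS, MoCA, cluster rating, English and no concurrent therapy. On that reading 'appropriate' simply means eligible, and approach follows assessment order. The supervisor assesses these referrals anyway as routine work. The flowchart, which may hold recruitment detail, cannot be seen.

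Much of this stands, but it does not remove the need for a rule. If every eligible client is offered the study in turn, the method is close to consecutive and the convenience label is wrong. If not, there is unrecorded discretion. One sentence is needed in either case.

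A second reply is that inference is within case. Four baselines, reliable change, a sceptic brief and a three-person panel are meant to expose a client who would have improved anyway. The plan sets no success rule based on a count of improvers, so probabilities for such a count would not describe this study. This also stands. Selection on good prognosis need not inflate attribution to ACT, and could favour non-ACT explanations.

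A reader might also infer a filter for promising cases from the phrase "any referral that is felt would benefit from individual clinical psychology sessions". The documents do not support that. In Screening and baseline the phrase explains who is referred for individual psychology in general. It is neither a study selection step nor a forecast of response to ACT, and consecutive offer would leave it in place.

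**Conclusion.** The point holds in a limited form. The protocol names convenience sampling, leaves the screening term undefined where it is used, and in its readable text sets neither an order of approach nor a record of eligible clients not approached, for initial places or replacements.

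The stronger conclusion, that the series is hand-picked for good prognosis, is one a reader might draw, but no section says so. What can be said is that nothing prevents or reveals such a choice. The harm falls on the cross-case efficacy statement and on generalisation, and less on attribution within each case.

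Its size cannot be calculated from the documents. Under the assumed inputs above it runs from nothing (four eligible clients) to about half an SD of prognosis (four from twelve, r = 0.5). This is an inexpensive improvement, not a defect that undermines the individual case analyses. It rests on the readable text, with the flowchart unseen.

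**What to change.** - **Sampling technique:** replace convenience sampling with consecutive offer. Every psychology referral meeting the listed inclusion and exclusion criteria is offered the study in order of assessment while a place is open, replacements included.
- **Study Setting:** state that 'appropriate' means meeting the criteria in the Eligibility Criteria section. Name that section, because the shorter list in the Study Summary differs (it still asks for ability to travel to the service).
- **Reporting:** keep an anonymised log and report the numbers assessed, eligible, approached, declining and consenting, with reasons.
- **If the order cannot be kept:** limit the efficacy wording to the selected cases.

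The cost is protocol wording, a short log and slightly less freedom over who fills a place. The planned number stays at up to four. Extra burden should be small, since the supervisor already does most of the initial assessments and HADS, MoCA and cluster rating are routine at the service. That is an inference, as the documents give neither referral flow nor therapist capacity. The July 2020 limit on a fourth participant need not be affected, because any eligible client may take an open place.

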The purpose of the study is to examine whether ACT can be an effective intervention in increasing quality of life in older adults (aged 65+), presenting to older adult mental health service with psychological difficulties, as well as why ACT is effective.

PRIMARY OBJECTIVE

In this study we aim to investigate the efficacy of ACT for supporting older adult clients experiencing psychological distress.

SECONDARY OBJECTIVE(S)

In addressing the primary objective, we will be guided by three fundamental questions: (1) Do (meaningful) changes occur for client-participants over the course of ACT intervention? (2) Are observed changes broadly attributable to the ACT intervention? (3) What specific factors (ACT-specific, non-specific, extra-therapeutic) contribute to observed changes?

The study will also identify adaptations that may be facilitative of change when using ACT with older adult clients, **with consideration of the impact that moving the study to a telephone/videocall delivered intervention.**

OUTCOME MEASURES

PRIMARY OUTCOME MEASURE

1. Change in quality of life assessed using the Older People's Quality of Life questionnaire (OPQOL-brief; Bowling, Hankins, Windle, Bilotta, & Grant, 2013). Completed by participant.

SECONDARY OUTCOMES

Symptom measures

1. Client's level of cognitive functioning assessed using the Montreal Cognitive Assessment (MoCA; Nasreddine et al., 2005). Completed by MHSOP team with the participant.
2. Changes in symptoms of anxiety and depression assessed with the Hospital Anxiety and Depression Scale (HADS; Zigmond & Snaith, 1983). Completed by the participant.

Change measures

1. Change in/progress on client's goals assessed using the Simplified Personal Questionnaire (PQ; Elliot, Mack, & Shapiro, 1999). Completed by participant with guidance from therapist.
2. Client's attribution of change and view on therapy assessed with the Change Interview (Elliott, Slatick, & Urman, 2001). Conducted by secondary researcher with participant.

Process measures

1. Change in psychological flexibility assessed using the CompACT-8 (Morris, Dawson, & Golijani-Moghaddam, 2019). Completed by participant.

Session measures

1. Change in client's weekly level of quality of life assessed using the Outcome Rating Scale (ORS; Miller, Duncan, Brown, Sparks & Claud, 2003). Completed by participant.
2. Change in therapeutic alliance assessed with the Session Rating Scale (SRS; Duncan et al., 2003). Completed by participant.

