3. Client's (qualitative) views on individual therapy sessions assessed with the Helpful Aspects of Therapy form (HAT; Lewlyn, Elliott, Shapiro, Firth, & Hardy, 1988). Completed by therapist in discussion with participant.

Fidelity measure

1. Adherence to ACT related processes assessed with the ACT Fidelity Measure (ACT-FM; O'Neill, Latchford, McCracken & Graham, 2019). Completed by therapist and secondary researcher.

EXPLORATORY OUTCOMES

Adaptations made to treatment will be recorded so that commentary can be made on what adaptations to ACT may be beneficial for older adult clients. **Consideration of the impact that delivering the intervention in a remote manner will also be made and any adaptations that were made to facilitate this.**

TABLE OF OUTCOMES

Objectives	Outcome Measures	Timepoint(s) of evaluation of this outcome measure (if applicable)
Primary Objectives	1. Quality of life (OPQOL-brief).	1. Baselines, pre-, mid- and post-intervention, and at six-week follow up.
Secondary Objectives	Symptom measures 1. Cognitive functioning (MoCA). 2. Changes in levels of anxiety and depression (HADS).	1. At initial contact, by service as standard practice. 2. At initial contact, by service as standard practice. Baselines, pre-, mid- and post-intervention,

		and at six-week follow up.
	Change measures 
 1. Client's goals (PQ). 2. Client's view on change (Change Interview). 	
 1. Prior to each weekly treatment session. 2. One week after finishing treatment.
	Process measure 
 1. Psychological flexibility (CompACT-8). 	
 1. Baselines, pre-, mid- and post-intervention, and at six-week follow up.
	Session measures 
 1. Quality of life/general outcomes (ORS). 2. Therapeutic alliance (SRS). 3. Client's views on the therapy session (HAT). 	
 1-3. At the end of each weekly treatment session.
	Fidelity measures 
 1. Fidelity of treatment (ACT-FM). 	
 1. At the end of each session (by therapist) and random sampling of all sessions (by Secondary Research Supervisor).

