Therapy will use the above protocol as a guide for treatment; however, duration and content will be adapted based on the individual. Primarily this will be using extra sessions to focus on any content that participants may need further work with, but could also include a break in the middle of sessions. Sessions will predominantly be weekly and one hour in length, dependent on any required adaptations. Sessions will be delivered either over telephone or via QHealth. As ACT is a processes-based therapy, rather than a single manualised procedural treatment, adherence to a strict protocol is not theoretically mandated (Hayes & Hoffmann, 2017).

The basic structure of each session will be:

1. Participant completes weekly Personal Questionnaire before session.
2. Session begins with a mindfulness exercise.
3. Homework and concepts from previous session are reviewed.
4. New material for the session is covered.
5. Homework is assigned.
6. Therapist completed HAT with participant.
7. Participant is supported to complete ORS and SRS.

Following each session, the student researcher will receive clinical supervision with [name] by (secure) videocall or telephone to discuss any relevant case information, such as

risk and progress. A clinical note will be made on the participant's electronic case record, as in standard practice. The student researcher will also receive regular ACT supervision from [name], Secondary Research Supervisor/Chief Investigator to address any modality specific questions or dilemmas. Relevant discussions from this will be added to the participant's electronic case record as required.

At mid-point in therapy (usually session six), QP1.1 will be repeated at the start of the therapy session. QP1.1 will also be repeated at the final therapy session to act as the post-therapy time point.

During the final session, the PQ will be re-administered to determine whether there has been any change in their problem areas. Participants will also be given the opportunity to 're-author' their problem areas. This is to capture any theoretical change they may have occurred in identifying where problems at situation, as would be posited by the ACT theoretical framework (living with problems, rather than eliminating them). Participants will complete any required session questionnaires prior to filing in the PQ.

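### The ORS is defined as a weekly quality-of-life rating but is always taken at session end, so change over the week cannot be cleanly separated from reaction to that session

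*Combined protocol and SAP*

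**What the plan says.** - **Construct.** Secondary Outcomes, session measures: "Change in client's weekly level of quality of life assessed using the Outcome Rating Scale".
- **Timing.** The Table of Outcomes gives one time point for the ORS, the Session Rating Scale (SRS) and the HAT together: "At the end of each weekly treatment session".
- **Order within the session.** In the basic session structure under Study Regimen, step 1 is "Participant completes weekly Personal Questionnaire before session". The mindfulness exercise, homework review, new material and homework setting follow. Step 6 is "Therapist completed HAT with participant" and step 7, the last, is "Participant is supported to complete ORS and SRS".
- **Regimen text.** Under Screening and baseline: "Participants will be supported to complete questionnaires after the session which will have been posted out to them".
- **Final session.** "Participants will complete any required session questionnaires prior to filing in the PQ". The ORS is not moved to the start there either.
- **Spacing.** "Sessions will predominantly be weekly and one hour in length", subject to individual adaptation.
- **Use in the analysis.** Table 1 area 3 (within-therapy process-outcome correlation) correlates ACT adherence with the ORS and with the PQ, which that table calls the SPQ. It is offered as evidence that process varies with the client's week-to-week change. The Table of Outcomes has the therapist rate adherence at the end of each session, with a random sample rated by a second person.
- **Schedule.** Session measures run from Session 1 (week 4) to Session 12 (week 15). No ORS is scheduled before a session, during the baselines, at the Change Interview (week 16) or at follow-up (week 20).

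**The concern.** A rating meant to describe the week is collected just after an hour of therapy and a discussion with the therapist about what was helpful. A good session may then look like a good week, and a distressing one like a bad week. The plan takes its other weekly measure, the PQ, before the session and gives no reason for treating the ORS differently.

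The place where this matters is Table 1 area 3. Adherence and the ORS are both recorded at the end of the same hour, so an association between them may be a reaction to that hour. The protocol requires evidence in at least two of five areas before a case goes to adjudication, so area 3 can supply one of the two. The timing also makes it harder to rule out a rival explanation that the protocol lists in Table 2, namely relational artefacts.

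**Working it through.** The plan states no figure that depends on this point. The check sets the sections side by side and then follows what each ORS score contains.

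**1. Are the sections consistent about timing?** Yes. The Table of Outcomes, the regimen text and the session structure all put the ORS after the session content. The session structure also puts it after the HAT. With up to 12 sessions, 12 of 12 scores per client are post-session. Over up to four clients that is at most 4 × 12 = 48 scores, with no pre-session score.

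**2. What does a score contain?** As a working assumption (additive, not taken from the documents), let W_k be the client's level over the week before session k, S_k the immediate reaction to session k, and A_k the adherence rating at session k. Leaving out measurement error:

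- Score: ORS_k = W_k + S_k
- Change: ORS_k − ORS_(k−1) = (W_k − W_(k−1)) + (S_k − S_(k−1))

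If S is the same at every session, the second bracket is zero. A constant added to every score also leaves a correlation unchanged. Only variation in S from session to session does harm. The documents give no information on that variation.

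**3. What does area 3 then estimate?** Table 1 does not state the pairing. Read as same-session pairs:

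Cov(A_k, ORS_k) = Cov(A_k, W_k) + Cov(A_k, S_k)

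The first term concerns a week that ended before session k. The second concerns the hour just finished. What bears on the week after session k is Cov(A_k, W_(k+1)), which is neither term. Pairing A_k with the current ORS at session k+1 would bring in W_(k+1), but also S_(k+1).

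**4. What would a pre-session ORS give?** Then ORS_k = W_k, and A_k can be paired with ORS_(k+1) = W_(k+1). For 12 sessions, k runs from 1 to 11, so there are 12 − 1 = 11 pairs per client, against 12 same-session pairs now. A reading at the week 16 Change Interview, one week after session 12, restores the twelfth pair. The ORS at session 1, taken before any ACT content, would be the one reading made before therapy starts.

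**5. What is untouched?** The OPQOL-brief is taken at four baselines (the fourth serving as pre-therapy), mid-therapy, post-therapy and follow-up, and does not depend on where the ORS sits. The weekly PQ is taken before the session. At the final session, however, the PQ is re-administered after the session questionnaires, so the contrast between PQ and ORS holds for the weekly PQ and not for that administration.

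**The case against.** The strongest reply is that this is one secondary scale, filed under session measures, and that Table 1 names it only in area 3, where the pre-session PQ stands beside it. Quality of life is carried by the OPQOL-brief. Baselines and follow-up are collected by Assistant Psychologist calls, and the mid-therapy pack is given at the start of the session. The sceptic brief looks for relational artefacts, reactive effects and replication across measures, so a post-session lift can be argued before the panel. The ORS recall instruction is not reproduced, and the schedule refers to a timetable of individual measures that is not in the text available. All of this stands, and it limits the weight of the point. It does not remove the mismatch between construct and timing, and none of these safeguards supplies a pre-session ORS.

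A reader might infer more than the documents support:

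- **That the ORS series cannot show any change in life outside therapy.** The outcome is worded as a weekly level and makes no separate claim about life outside therapy. Mixing weakens the inference without making it impossible.
- **That a post-session lift must survive in change scores.** A constant lift cancels, and the size of any varying part is unknown.
- **That the SRS colours the ORS.** The two share step 7 and no order between them is given. Only the HAT clearly comes first.
- **That moving the ORS would supply an untreated baseline series.** It supplies one pre-therapy reading. From session 2 onward a pre-session score still follows earlier treatment.

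It is also fair to object that the change is not free. Area 3 needs a stated lag, the last session loses its following ORS, and several sections must be brought into line.

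**Conclusion.** The point holds in a limited form. The ORS is defined as weekly, but every score is taken after the session content and the HAT discussion. Session-to-session ORS change, and the area 3 correlation with same-session adherence, therefore cannot cleanly separate change over the week from an immediate reaction to the session.

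The extent is all of the up to 12 scores per client. The size of the bias cannot be derived from the documents and could be small. The conclusion rests on the stated order of steps and on the protocol's description of the ORS as weekly. The reading of area 3 further assumes same-session pairing, which is the natural reading but is not written down. The primary outcome and the weekly pre-session PQ are not affected. The change is worth making because it costs little.

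**What to change.** 1. In the basic session structure, move the ORS to step 1 beside the PQ. At session 1, complete it before any ACT content. Leave the SRS and HAT at the end.
2. Align the Table of Outcomes (ORS before each session; SRS and HAT at the end), the regimen sentence on questionnaires after the session, and the final-session order, so that an ORS and a PQ are both taken before session 12.
3. In Table 1 area 3, state the pairing: adherence at session k with the ORS and PQ taken before session k+1.
4. Decide whether to complete one further ORS at the existing week 16 Change Interview contact.

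**Cost.** The form is the same, and so is the number of completions (12 for a client who has all sessions). Without item 4, no ORS follows session 12 and area 3 has 11 pairs per client. With it, there are 12 pairs for one extra completion (13 in all).

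**If the current timing is kept**, describe the ORS as a post-session rating in Secondary Outcomes and in the Table of Outcomes. State that its same-session correlation with adherence will not be counted as evidence of week-to-week change.
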